### **Organizational structure of the study team**

The study was proposed by the Nell Hodgson Woodruff School of Nursing at Emory University, the academic home of the PI/PD, [name]. Although there are investigators involved from a number of institutions and organizations, Emory is the sole site for all research activity associated with the study, and therefore the Emory IRB is the only IRB involved in providing oversight for human research activities. The study is funded by the National Institute on Aging at NIH. The overall goal of the study – and therefore the expectation of the funding agency – is the successful demonstration of an internet-based system that will enable organizations such as state agencies or private entities (e.g., health systems or churches) to implement an evidence-based dementia family caregiver psychoeducation program (the Savvy Caregiver) and make it available to their constituents. The system will include an organizational on-boarding component, a component that will enable the organizations to adapt the Savvy Caregiver to fit the values and customs of their constituents, and a large component designed to train Savvy Caregiver program leaders. The project involves investigators from Emory and also from the University of Buffalo, the University of British Columbia, and two private organizations, HealthCare Interactive, and Family Care Strategies, LLC. Each of the investigators will play three main roles: 1) collaborate in the development of the system; 2) assist in identifying entities (organizations) that would be willing to engage in two phases of testing of the system; and 3) assist in reviewing and interpreting the results

of the evaluation of system feasibility, acceptability, and preliminary efficacy that the Emory team will conduct. As described in the grant application budget, funds flow, per subcontract, to the home institutions/organization of the collaborating investigators to support their roles in the project.

### **Setting and location**

The first phase of the study, linked to Aim 1, does not involve human subject research. It only involves the study team, key consultants, and expert advisors who will work at their respective institutions.

The phase 2 and 3 studies are conducted from a single site, the School of Nursing at Emory University. We will centrally and via Zoom videoconferencing software (from Emory) consent the organizational leaders, interventionists trained by the system we developed and dementia family caregivers engaged in Savvy Caregiver programs provided by system-trained interventionists to participation in a wait-list design study in which caregivers from each site will be randomly assigned to immediate participation in a Savvy program offered by one of the newly trained interventionists or to delayed participation in Savvy (after 4 months). Each participant will be asked to complete the same post-program participation survey via Zoom videoconferencing software (from Emory) as in the Phase 2 study, and each will be asked to take part in four phone or video interviews in which Emory staff will administer well-established and validated questionnaires to assess burden, depression, anxiety, and caregiver competence and mastery as well as care recipient well-being. As in the phase 2 study, a sub-sample of caregiver participants (N=18) will be asked to participate in semi-structured interviews – also completed via Zoom videoconferencing software - focused on their perceptions of the interventionist's program leadership skills, any adaptation experiences, and on ways in which they met their own needs and expectations. In both phases (2 and 3) organizational leaders and system-trained

interventionists will be asked to take part in qualitative formative evaluation interviews conducted by Emory study staff.

## **Population to be studied**

### *Inclusion Criteria:*

#### *Organizational Leaders*

- a) Able to understand and speak English
- b) Affiliated with an organization serving caregivers for family members living with Alzheimer's disease or related dementias
- c) 18 years or older

#### *Interventionists*

- a) Able to understand and speak English
- b) Affiliated with a participating organization
- c) 18 years or older

#### *Caregivers*

- a) Able to understand and speak English
- b) Caregiver for a person living with Alzheimer's disease or related dementias (PLWD) who is providing informal care for at least 3 hours a day. PLWD should not be bound for institutional care within the next 6 months.
- c) 18 years or older

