The number of PLWD in the U.S. will rise from 5.7 million to 14 million by 2050, and the number of family caregivers who maintain these persons in the community will rise proportionately from 15 million at present. Several psychoeducation programs, including Savvy, have successfully ameliorated the adverse effects of caregiving, but these programs are only minimally available and accessible. Present in 15 states, principally through Administration for Community Living support, Savvy has served more than 15,000 caregivers over the last decade; this represents only one one-thousandth of the U.S. caregiver population. So far, Savvy has been exclusively disseminated through on-site in-person interventionist training by Savvy authors. This costly procedure has limited dissemination to large agencies that have obtained external grant support. The development of this proposed web-based system will take advantage of ubiquitously available distance education methods and platforms to greatly expand access to Savvy for the many organizations, especially small and local organizations that serve the growing number of diverse PLWD and their family caregivers. The activities proposed focus principally on developing and testing the preliminary efficacy of the web-based system. Manuals, slides, handouts, and workbooks will be concurrently developed/revised to harmonize with the system and guide organizations in administering the Savvy program.

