#### **4. Goals/Aims**

*Aim 1.* Develop a prototype web-based system for Savvy interventionist training and certification and an accompanying performance fidelity monitoring process. Development efforts will yield web-based components delivered through freely available course management and survey applications (e.g., Canvas; Articulate Rise) that will enable sponsoring entities to train and certify interventionists who can locally tailor Savvy, monitor the fidelity of their performance in delivering Savvy, and assess the program's impact on caregivers.

*Aim 2.* Establish the field-readiness of the system. We will engage three community entities serving culturally, ethnically, and geographically diverse constituencies to collaborate with the study team and expert advisory panel in a highly participatory formative test of the prototype system developed through Aim 1 activities. Results and feedback will inform finalization of materials for the Aim 3 trial.

*Aim 3.* Conduct a field trial of the system. The trial will test the effectiveness of the system and examine its preliminary efficacy in producing expected outcomes (i.e. well-being, mastery) in a diverse group of caregivers participating in programs delivered by newly trained interventionists. Six culturally or organizationally diverse sponsors will recruit 2 individuals each to be trained as Savvy interventionists (12 interventionists) and each sponsor will then recruit at least 20 caregivers to take part in a wait-list, no control group study (N=120) of the performance of the interventionists and the preliminary efficacy of the Savvy program provided by them.

The figure below provides a broad timeline for project activities. While we will begin some Aim 2 activities before all of the Aim 1 activities are complete and some Aim 3 activities before all of the Aim 2 activities are complete, we expect Aim 1 activities to be complete by project month 12 and Aim 2 activities to be complete by the end of the second project year.

		Year 1	Year 2	Year 3	Year 4
Project startup activities	Project startup activities	Start			
	Preliminary Syllabus & Materials	Start	End		
	Storyboard Content & Delivery		Start		
	Materials Production		Start		
Recruit/orient 3 organizations	Recruit/orient 3 organizations				
	Train interventionists		Start		
	Interventionists provide Savvy		Start		
	Evaluate & revise		Start		
Recruit 6 organizations	Recruit 6 organizations				
	Train interventionists			Start	

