### *Exclusion Criteria:*

Not applicable.

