## **Recruitment**

Each of the three types of recruitment and retention efforts is described below:

*Sponsoring Organizations.* We seek to recruit 3 organizations for our Aim 2 activities and 6 organizations for our Aim 3 activities; the Aim 2 organizations will be able to continue as Aim 3 organizations. Since these sponsoring organization leaders will be involved in the Aim 2 and 3 studies, we will seek their informed consent for participation in the studies. We are specifically seeking to recruit organizations serving the targeted minority groups, as well as those serving a more mixed or majority clientele. Several of the study team members and program advisors are either directly involved with or have strong contacts with potential sponsoring organizations, and we have already identified preliminary organizational interest in taking part in the project. Beyond those specific contacts, the project Co-PIs, [name] and [name], can draw on their extensive networks for organizational recruitment. Past experience with organizations that have adopted Savvy testifies to the long-lasting involvement with the program: once adopted, Savvy remains a regular part of the organization's portfolio, so we do not expect organizational retention to prove a problem. Procedures in our Aim 2 and 3 approach involve considerable interaction between the project team and sponsor organization leadership, including the provision of information and feedback that can help these organizations to improved Savvy uptake among their clients. This interaction will also promote retention in the project.

*Interventionists.* It will be the sponsoring organizations who will identify individuals – from their existing staff or from volunteers whom they recruit – to be trained as Savvy interventionists by the system we develop and to lead Savvy programs that the sponsors organize. Guided by orientation and administrative materials and protocols that we will provide, the sponsors will organize the training, organize the Savvy programs, and conduct regular debriefings with the interventionists. Since these interventionists will be involved in the Aim 2 and 3 studies, we will seek their informed consent for participation in the studies. In

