addition to sponsor-based debriefings, the semi-structured interviews we will conduct with the interventionists during the Aim 2 and Aim 3 studies will also provide a linkage for them to the overall study and will, hopefully, provide them with a sense of ownership in the developing system.

*Caregivers.* It will only be family caregivers who will be part of the clinical trial component of this study (in Aims 2 and 3). Recruitment into the studies will be through referral from the sponsoring organizations. Each organization will recruit caregivers to take part in Savvy programs provided by interventionists trained in the system we are developing. We will provide organizations with materials they can use to announce Savvy and the studies; we will encourage the organizations to insert these materials into their own standard informational templates (i.e., standard logo and graphics). For caregivers willing to do so, their contact information will be provided to the Emory study team. We will arrange a phone or video call with each during which we will explain the study (Aim 2 or Aim 3 – a caregiver will not be able to take part in both), explain eligibility criteria, and seek informed consent (verbally) for participation. We do not anticipate attrition to be a problem in the Aim 2 study; research contact, following consent, will occur over a very brief period of time. All who consent to the Aim 2 study will take part immediately in a Savvy program and in an on-line survey and (for some) in-person interview conducted by phone or video right after the program. Prolonged retention will be more of a challenge in the Aim 3 study. Those taking part will enter a Savvy program either immediately or after a delay based on scheduling at the individual agencies. For those taking part immediately a series of 3 phone or video interviews will bracket their Savvy participation (at baseline then at 3 and 6 months following baseline. For those with a delayed start, we will conduct 4 interviews (upon sign up, immediately prior to the start of the program and then 3 and 6 months after program completion). To foster engagement with the project, we will prepare and distribute to participants a monthly project newsletter,

featuring tips on exercise and healthy eating and profiles of the study team. We will also send birthday and seasonal holiday cards, as appropriate.

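### Aim 3 caregiver eligibility admits graduates of non-study Savvy programs and several caregivers of one person with dementia, and outside Savvy during the wait is neither restricted nor recorded, so the wait-list contrast could be attenuated by an unknown amount

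*Combined protocol and SAP*

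**What the plan says.** Under Population to be studied, a caregiver must understand and speak English, be 18 or older, and look after a PLWD who is not about to enter institutional care within 6 months, as someone "who is providing informal care for at least 3 hours a day". The whole of the Exclusion Criteria section is "Not applicable".

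The only bar on earlier exposure is under Recruitment, where the choice is between Aim 2 and Aim 3: "a caregiver will not be able to take part in both".

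Field Methods randomizes individual caregivers once an organization has a cohort of 20, either to start at once or to start after 4 months. Section 10 models a random participant effect and a fixed cohort effect; it names no household or PLWD term. Its primary contrast uses 0m-2m. It also uses the delay group's 0m-2m-4m data to look for placebo effects and decline, and that group's 4m-6m change for the combined effect.

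On how available Savvy is, Section 3 reports that "Savvy has served more than 15,000 caregivers over the last decade", which it puts at one one-thousandth of U.S. caregivers. Recruitment says of past adopters that "once adopted, Savvy remains a regular part of the organization's portfolio", and that "the Aim 2 organizations will be able to continue as Aim 3 organizations".

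The baseline form, as described under Measures, covers socioeconomic status, PLWD information, length of caregiving and co-residence. It names no earlier caregiver training.

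**The concern.** A wait-list contrast depends on the delayed arm being unexposed while it waits, and on participants being able to gain from the program. Three kinds of caregiver could weaken this under the rules as written:

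- a caregiver who completed Savvy outside this project and keeps some of the benefit;
- two caregivers of the same PLWD, such as a spouse and a daughter, one starting at once and sharing what is learned with the other, who is waiting;
- a waitlisted caregiver who joins a non-study Savvy group at the organization before the assigned start.

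The stake is interpretation. Section 10 treats improvement in caregivers as evidence that system-trained interventionists deliver Savvy faithfully. A contrast shrunk by earlier or outside exposure could be taken as a shortcoming of the training system. If exposure is not recorded, the analysis cannot tell the two apart.

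**Working it through.** **The plan's own figure.** Section 4 gives six sponsors with at least 20 caregivers each: 6 x 20 = 120, which agrees with the stated N. The documents give no effect size, SD, allocation ratio or power, so everything below is illustrative. Assumptions: 1:1 allocation (60 per arm), SD = 1, two-sided 5% level, normal approximation.

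**Reference effect.** Effect detectable with 80% power = (1.960 + 0.842) x sqrt(2/60) = 0.511 SD.

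**Route 1, non-study graduates.** If a share p have completed Savvy and keep a fraction r of the benefit, the average effect is d(1 - p x r). For p = 10% and r = 0.5 to 1, the factor is 0.95 to 0.90; for p = 20%, it is 0.90 to 0.80. Randomization places graduates in both arms, so this is a smaller average effect in the people enrolled and not a bias between arms. Section 3's national figure is 15,000 / 15 million = 0.001; with r = 1 the factor would be 0.999.

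**Route 2, two caregivers of one PLWD.** Under an assumed 10:10 split of a cohort of 20, once one member is placed, 10 of the 19 remaining places are in the other arm: 10/19 = 53%. This is conditional on such a pair enrolling. If a share s of caregivers come in pairs and a fraction f of the effect spills over, the contrast is d(1 - s x 10/19 x f). Ignoring correlation within pairs:

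| s | Wait-list exposed | Power, f = 0.5 | Power, f = 1 |
|---|---|---|---|
| 10% | 5.3% | 77.9% | 75.6% |
| 20% | 10.5% | 75.6% | 70.8% |

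**Route 3, outside Savvy during the wait.** If a share c of the wait-list receives Savvy within the contrast window, the contrast is d(1 - c).

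**Routes 1 and 3 together**, with g = p x r and diluted effect 0.511 x (1 - g) x (1 - c):

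| g | c | Effect | Power at N = 120 | N for 80% power |
|---|---|---|---|---|
| 0 | 0 | 0.511 | 80.0% | 120 |
| 10% | 0 (or g = 0, c = 10%) | 0.460 | 71.3% | 150 |
| 10% | 10% | 0.414 | 62.1% | 184 |
| 20% | 10% | 0.368 | 52.3% | 232 |
| 20% | 20% | 0.327 | 43.4% | 294 |

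**Timing of route 3.** For the 0m-2m contrast, only Savvy received by month 2 counts. Attendance between months 2 and 4 leaves that contrast alone but reaches the other analyses. It could look like a placebo effect, or hide decline, in the delay group's 0m-2m-4m data. It also means the 4m value is no longer a pre-Savvy baseline for the 4m-6m change. Section 5 describes a different schedule, in which the delay group's second interview falls just before its program; on that schedule, attendance at any time in the wait would reach that measurement.

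**The case against.** Several stronger readings are tempting, and the documents do not support them.

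- *The contrast is diluted.* No rate of earlier exposure, shared PLWDs or crossover is given. Dilution is a risk of unknown size, and the 10% and 20% rows above are assumptions.
- *A pool of 15,000 graduates means many will enrol.* Section 3 itself equates that number to one in a thousand caregivers, and says dissemination was limited to large, grant-supported agencies, while the new system is aimed especially at small and local ones.
- *Any past Savvy participant can enter.* Aim 2 participants cannot, even where their organization continues into Aim 3. The gap is for graduates of earlier or non-study programs.
- *Graduates bias the comparison.* They fall in both arms. In a field trial of ordinary agency referrals, admitting them can be defended as a choice of target population.
- *The whole 4-month wait threatens the primary contrast.* Only the first 2 months do. Nor does the remark about past adopters show that a new sponsor with two trainees runs extra groups in that time.

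Two further points are fair. The Caregiving History form is not reproduced and might ask about earlier training. Section 5 makes system effectiveness the principal question and caregiver efficacy preliminary, and Section 10 would use unfavourable outcomes to guide further development.

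These points cut the likely size and the certainty, but they do not close the gap. Organizations are sought partly through the team's contacts and networks, and caregivers come by referral from those organizations, so exposure at some sites could exceed the national rate. No text covers caregivers of the same PLWD or outside attendance during the wait.

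**Conclusion.** The gap stands and is worth closing; its effect is possible attenuation that cannot be sized from the documents. Non-study graduates would lower the average effect without biasing the arm comparison. Spill-over between caregivers of one PLWD, and outside Savvy attended within 0-2 months, would bias the primary contrast toward zero. Later outside attendance would distort the secondary analyses of the delay group.

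The illustrated range runs from no loss, if all rates are zero, to 43.4% power in place of 80% if g and c are both 20%. It rests on 60 per arm, a true effect of 0.511 SD and the assumed rates. The national figure suggests that earlier exposure may be rare except at organizations that already offered Savvy. The low cost of the remedy, more than any demonstrated loss, makes the case for it. Confidence is medium.

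**What to change.** Replace the empty exclusion entry for Aim 3 caregivers with two criteria:

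1. No earlier participation in any Savvy program, including online versions.
2. One enrolled caregiver per PLWD. If that is too restrictive, randomize caregivers of the same PLWD together and add a household term to the Section 10 model.

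In addition, ask organizations not to place waitlisted study caregivers in non-study Savvy groups before their assigned start, and ask at each interview about any Savvy attendance outside the study, so that exposure can be reported and examined in a sensitivity analysis.

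The cost is two questions at the existing eligibility call, one interview item and one request to organizations. The downside is that a few interested caregivers per organization become ineligible, which may slow the filling of cohorts of 20. The joint-randomization option keeps relatives in, at the price of a slightly more complex allocation and model.

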### *Exclusion Criteria:*

Not applicable.

## **Community Participation**

In developing the adaptation element for the interventionist training system, we will employ established models for adapting evidence-based programs. The starting point for these models is an anchoring in an understanding of a program's theory-base and mechanism and the key parts of the program. Such anchoring is central to the organizational on-boarding and interventionist training system. The adaptation models then use dialogue with end users to accomplish adaptation. The adaptation element we will develop will train interventionists to identify concerns among Savvy participants or possibly within the larger community about Savvy terms, concepts, or delivery processes and to arrive at "translation" that makes Savvy more available and acceptable to the populations they serve while maintaining the integrity of the core principles and mechanisms. For example, Savvy originally stressed that caregivers gradually have to assume more control of the care recipient's behavior. Through interactions with caregivers from a variety of backgrounds and advocates of person-centered care, we now speak in terms of a caregiver's need to provide more guidance (or assume more responsibility) for what the person does during the day. Savvy interventionists in Hawaii are finding that adding a "session zero" – a prelude to Savvy – allows Native Hawaiian elders to engage in "talk story," a culturally important process that sets the stage for these elders to give permission to (typically) younger interventionists to train and coach them. No core principles are bent in either case, but the adaptations promote learner receptivity. An adaptation team, consisting of key study team faculty ([name], [name], and [name]) and the project's Master Trainer consultants ([name] [name], [name], and [name]) will take the lead in formulating the content and delivery method for this training element.

